physiotherapist and the family under the control of the physiotherapist. Family-centered physiotherapy practices have come to the fore in recent years, and are a treatment approach applied by the family that focuses on the environment and what the child can do. Motor reactions are activated by providing normal sensory input. Telerehabilitation is the provision of rehabilitation services by rehabilitation specialists with computer-based technologies and communication tools. It is a developing method that provides rehabilitation services by reducing time, distance and cost barriers and using technological tools. There are previously studies on a portable smart system that is monitored remotely and created for early assessment and intervention.

Although the importance of early physiotherapy approaches is known today, when the literature is examined, it is seen that the number of studies is insufficient and there is no consensus yet on which therapy approach is more successful. No previous study has been found in which family education of risky babies was followed up with telerehabilitation.

2. Objectives

Primary Objective

Evaluate the effectiveness of family-centered, goal-directed early physiotherapy approaches in high-risk infants using telerehabilitation.

Secondary Objectives

- 1. Compare the motor, cognitive, and language developmental progress of infants in telerehabilitation and single-session education groups.
- 2. Assess family satisfaction with telerehabilitation-based physiotherapy.
- 3. Measure neurological outcomes using Hammersmith Infant Neurological Examination (HINE).
- 4. Determine the achievement of individualized treatment goals using the Goal Attainment Scale (GAS).

3. Study Design

Type of Study

A prospective, randomized, controlled trial conducted at the Risky Infants Polyclinic.

Duration

12 weeks, with evaluations conducted at baseline, 4th, 8th, and 12th weeks.

Groups

- 1. **Telerehabilitation-Based Group**: Families received exercise training in the clinic, followed by weekly real-time video-conference sessions (1 day/week) and follow-up phone calls (2 days/week).
- 2. **Single-Session Education Group**: Families received a single session of exercise training in the clinic and were asked to continue the exercises independently.

4. Participants

Inclusion Criteria

- Premature infants (<37 weeks) treated in neonatal intensive care units.

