- Infants with neurological abnormalities (muscle hypertonia, hypotonia, overstimulation, abnormal general movements, or cranial ultrasound abnormalities).
- Infants aged 0-12 months (corrected age for prematurity applied).
- Diagnosed as at-risk for motor or developmental delay.
- Infants whose medical treatments are complete and are no longer in neonatal intensive care.
- Families who agree to participate and provide informed consent.

Exclusion Criteria

- Infants with congenital cyanotic heart disease, cystic fibrosis, genetic diseases, or congenital anomalies.
- Infants on ventilators.
- Families unable to attend regular check-ups or weekly communication.
- Infants already enrolled in special education or rehabilitation centers.

5. Outcome Measures

Primary Outcomes

- 1. Changes in neuromotor development using the Hammersmith Infant Neurological Examination (HINE).
- 2. Cognitive, motor, and language development using Bayley III.
- 3. Goal achievement using the Goal Attainment Scale (GAS).

Secondary Outcome

4. Family satisfaction using a custom Satisfaction Survey.

6. Intervention

Training Protocol

- Exercises tailored to neuromotor developmental stages, delivered by experienced pediatric physiotherapists.
- Families instructed to perform exercises for 30-45 minutes, 3 days per week, for 12 weeks.
- Telerehabilitation group received one supervised video-conference session weekly, with phone call follow-ups for the remaining two days.
- Single-session group received instructions during one in-clinic session with no additional follow-up.

7. Data Collection and Tools

Demographics

• Collected using forms capturing infant and family data (age, education, marital status, economic status, number of children, etc.).

Developmental Assessments

- 1. **Bayley III**: Evaluates cognitive, motor, and language development.
- 2. **HINE**: Assesses cranial nerve function, posture, tone, reflexes, and orientation.
- 3. GAS: Tracks individualized treatment goal achievement.

Satisfaction Survey

Assesses family satisfaction with treatment.

8. Statistical Analysis Plan (SAP)

Sample Size Calculation

- Based on a similar study (Pineda et al., 2020), the effect size was calculated as 1.09.
- Using G*Power 3.1.9.2, a total sample size of 24 infants (12 per group) was determined for α =0.05 and power=0.95.

Statistical Methods

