• **Descriptive Statistics**: Mean, standard deviation, minimum, and maximum values for quantitative data; frequency and percentage for qualitative data.

• Group Comparisons:

- Mann-Whitney U and chi-square tests for continuous and categorical demographic data.
- Wilcoxon Signed-Ranks Test for pre- and post-treatment comparisons of Bayley III, HINE, and GAS scores.
- **Significance Level**: p<0.05.

9. Ethical Considerations

- The study received ethical approval from the relevant institutional review board.
- Signed informed consent obtained from all participating families.
- Data confidentiality and anonymity maintained throughout the study.

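### Section 8 plans no between-arm effect estimate or confidence interval for any outcome, and with 12 infants per arm a p-value alone could not rule out a large benefit

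*Combined protocol and SAP*

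**What the plan says.** Section 3 describes a randomised controlled trial with two groups, assessed at baseline and at weeks 4, 8 and 12. The first secondary objective in Section 2 is explicitly comparative: "Compare the motor, cognitive, and language developmental progress of infants in telerehabilitation and single-session education groups". Section 5 lists HINE, Bayley III and GAS as primary outcomes and a family satisfaction survey as the secondary outcome.

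Statistical Methods in Section 8 is short enough to list in full:

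- Descriptive statistics: "Mean, standard deviation, minimum, and maximum values for quantitative data; frequency and percentage for qualitative data". The line does not say whether these are given by group.
- Under Group Comparisons, first item: "Mann-Whitney U and chi-square tests for continuous and categorical demographic data".
- Under Group Comparisons, second item: "Wilcoxon Signed-Ranks Test for pre- and post-treatment comparisons of Bayley III, HINE, and GAS scores".
- A significance level of p<0.05, with no statement of sidedness.

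On sample size, Section 8 states that "the effect size was calculated as 1.09" from a similar study, and that "a total sample size of 24 infants (12 per group) was determined for α =0.05 and power=0.95". It does not say whether 1.09 is a between-group or a within-group effect size.

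**The concern.** A randomised comparison should produce an estimate of the difference between the arms and a statement of its precision. Section 8 provides neither. The between-group tests are tied to demographic data, and the outcome test compares each infant with itself.

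The absence of any between-arm outcome test is the more basic gap. The present point would survive its repair: extending the Mann-Whitney U test to the outcomes would add a p-value, but still no effect size and no interval.

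What is at stake is how the result can be used. In a trial this small, very different true effects are compatible with the same verdict at p<0.05. Without an interval, a reader cannot tell a result that is close to null from one that leaves a substantial benefit open. The background text before Section 2 says that existing studies are too few and that there is no consensus on approach. An estimate with an interval is what later trials and syntheses would need from this one.

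**Working it through.** **Inputs.** From Section 8: 12 per group, effect size 1.09, α = 0.05, power 0.95. Assumed, because the documents are silent: equal SDs in the two arms, a two-sided 5% level, and no loss to follow-up (10 per arm is shown as a variant). Differences are in SD units.

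**1. The plan's own figure.** Reading 1.09 as a between-group standardised difference, the normal approximation gives n per arm = 2 × (1.960 + 1.645)² / 1.09² = 2 × 12.996 / 1.188 = 21.9, so 22 per arm (44 in total). The t-based calculation gives 23 per arm (46 in total). One-sided, it is 19 per arm (38 in total). The stated 24 in total is not reproduced. The only variant found that gives 12 per group is a one-sided signed-rank test within one group with 1.09 as the paired effect size (power 0.963), and that is not a between-arm comparison. With 12 per arm and a between-group 1.09, two-sided t-test power is about 0.72, so the planned effect itself would be non-significant about 28% of the time.

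**2. Width of the interval that the plan omits.** Half-width = t(0.975, 2n − 2) × √(2/n).

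- 12 per arm: 2.074 × 0.408 = 0.847 SD
- 10 per arm: 2.101 × 0.447 = 0.940 SD

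With baseline adjustment at an assumed baseline-outcome correlation r, half-width = t(0.975, 21) × √(2/12) × √(1 − r²):

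- r = 0.5: 2.080 × 0.408 × 0.866 = 0.735 SD
- r = 0.7: 2.080 × 0.408 × 0.714 = 0.606 SD

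**3. What a non-significant result leaves open** (unadjusted, 12 per arm; positive values favour telerehabilitation).

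| Observed difference | 95% CI |
|---|---|
| −0.4 | −1.25 to 0.45 |
| 0 | −0.85 to 0.85 |
| 0.4 | −0.45 to 1.25 |
| 0.8 (p = 0.063) | −0.05 to 1.65 |

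A result is non-significant when the observed difference lies within ±0.847 SD. Its upper limit then runs from 0 to 2 × 0.847 = 1.69 SD. For any non-significant observed difference above 1.09 − 0.847 = 0.24 SD, the interval still contains the plan's own 1.09. With baseline adjustment the largest possible upper limit falls to 2 × 0.735 = 1.47 SD (r = 0.5) or 2 × 0.606 = 1.21 SD (r = 0.7), both still above 1.09.

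**The case against.** The strongest reply is that Section 8 contains no between-arm outcome p-value, so there is no between-arm non-significant result to misread, and the point is only a reporting detail of a larger omission. The first part is correct: the calculations above describe what would follow once a between-arm analysis exists. The second part does not follow, because adding a rank test alone would still leave the size and precision of the difference unreported.

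A second reply is that unadjusted precision is pessimistic. That is fair, and the adjusted range is shown for this reason. No adjustment is planned, however, and the adjusted intervals remain wide.

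Several stronger readings are tempting but not supported:

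- A reader might infer that 0.85 SD is the largest benefit compatible with a non-significant result. That holds only if the observed difference is exactly zero. The limit can be as high as about 1.69 SD, and it is below 0.85 SD when the observed difference favours the single-session group.
- A reader might infer that p>0.05 will be reported as showing that one session is enough because it is cheaper. The documents contain no interpretation rule, no equivalence or non-inferiority aim and no cost for either arm. The background text mentions cost only as a barrier that telerehabilitation reduces.
- A reader might infer that a significant result would overstate the benefit about twofold. That figure belongs to an assumed true effect of 0.5 SD (power 0.216, ratio 2.06). At 1.09, read as a between-group effect, the ratio is about 1.17. The exaggeration comes from low power and selection on significance. An interval shows the imprecision but does not remove it.
- Showing means and SDs beside rank tests is a matter of presentation, not an error.

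**Conclusion.** The point holds. Followed exactly, Section 8 yields no between-arm effect estimate and no confidence interval for any outcome, although Section 2 sets a between-group objective. The missing interval would extend about ±0.85 SD around the observed difference with 12 per arm, about ±0.94 SD with 10 per arm, and about ±0.74 to ±0.61 SD with baseline adjustment at an assumed correlation of 0.5 to 0.7. A non-significant result could therefore not by itself rule out a large benefit.

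These figures assume equal SDs and a t-based analysis. The correlations are assumptions, since the documents give none. The finding about the text itself, that no estimate or interval is planned, depends on none of them.

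The conclusion concerns p-values taken alone. Some non-significant results would be informative: an observed −0.7 SD would have an interval of about −1.55 to 0.15, which excludes any sizeable benefit. That is a reason to let the interval govern the wording, rather than to label every p≥0.05 result inconclusive.

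**What to change.** In Section 8, Statistical Methods, add for each outcome:

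1. The week-12 difference between the arms with its 95% confidence interval, adjusted for the baseline value where one is collected. If a rank test is used instead, give the Hodges-Lehmann shift with its exact 95% interval.
2. A statement that conclusions rest on the estimate and its interval, and that p≥0.05 alone will not be reported as 'no difference' or as equivalence.
3. A statement that descriptive summaries are given by arm. Medians and quartiles are an optional addition.

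This needs SAP wording and a few more table columns, with no extra infants or assessments. The downside is that the intervals will look wide, which is an accurate picture of what 24 infants can show.

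### The SAP tests demographics between arms but names no between-arm outcome model and no baseline covariate; with 12 per arm, those tests say little about comparability

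*Combined protocol and SAP*

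**What the plan says.** Section 3 describes the trial as "A prospective, randomized, controlled trial conducted at the Risky Infants Polyclinic" and mentions no stratification, blocking or minimisation. Section 4 admits "Infants aged 0-12 months (corrected age for prematurity applied)". Section 7 says of demographics: "Collected using forms capturing infant and family data (age, education, marital status, economic status, number of children, etc.)".

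In section 8, the between-group entry under Statistical Methods is "Mann-Whitney U and chi-square tests for continuous and categorical demographic data". Bayley III, HINE and GAS appear only under a Wilcoxon signed-rank comparison of pre- and post-treatment values. The pre-treatment score enters inside that paired test. Otherwise no baseline variable enters any outcome analysis, no model compares the arms on an outcome, and no action follows from a demographic p-value. Section 2 nevertheless sets comparison of the two groups' developmental progress as an objective.

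On size, section 8 says that "the effect size was calculated as 1.09" and that "a total sample size of 24 infants (12 per group) was determined for α =0.05 and power=0.95".

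**The concern.** If allocation is random, every baseline difference arises by chance. A significance test of such a difference flags close to its nominal rate of trials and answers no open question. In a trial this small, a non-significant result is also weak evidence that the arms are alike, yet readers tend to take it that way.

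Eligible infants span the whole first year of corrected age and the outcomes are developmental, so age is a plausible prognostic factor. The baseline score is a stronger candidate. A between-arm analysis that used both would not depend on how the randomisation happened to fall. The plan has no such analysis, so two things are at stake: the precision available from 24 infants, and protection of the estimate when a particular randomisation is uneven.

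**Working it through.** **Inputs from the documents:** 12 per arm, α = 0.05, effect size d = 1.09, eligible corrected age 0 to 12 months.

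**Assumptions:** two-sided tests; d is a standardised mean difference; ages normal, or uniform over 0 to 12 months (SD = 12/√12 = 3.46 months, so 0.5 SD = 1.73 months); age correlates r = 0.2 to 0.7 with both baseline and week-12 scores; baseline correlates ρ = 0.7 or 0.8 with week 12. The documents give neither r nor ρ.

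**1. The plan's own figure.** For a two-sample t-test the noncentrality is d√(n/2) = 1.09 × √6 = 2.67 on 22 df, which gives power 0.72 (0.83 one-sided). Power 0.95 needs 23 per arm (19 one-sided). So 24 infants at 0.95 does not reproduce as a two-group comparison. What follows uses only the stated 12 per arm and is not affected by this.

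**2. How often age is uneven.** The SE of the mean age gap is √(2/12) = 0.408 SD. P(|gap| > 0.5 SD) = 2[1 − Φ(0.5/0.408)] = 2[1 − Φ(1.225)] = 0.22. Simulation of 200,000 randomisations agrees (0.22 for normal and for uniform ages).

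**3. What the demographic test sees.** The exact two-sided Mann-Whitney test at 12 v 12 rejects when U ≤ 37 and flags about 4.5% of all randomisations. Among those with a gap above 0.5 SD it misses 79.7% (normal ages) or 79.9% (uniform). As a rough check, a test flagging exactly the most extreme 5% would miss 1 − 0.05/0.221 = 77%. Of trials that pass the test, 0.22 × 0.80 / 0.955 ≈ 18% to 19% still carry a gap above 0.5 SD.

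**4. What a gap does to an outcome comparison.** In SD units, an age gap g shifts the expected arm difference by:
- r·g for the unadjusted week-12 score;
- r·g − r·g = 0 for the change score;
- r·g − ρ·r·g = r(1 − ρ)g for ANCOVA on baseline;
- 0 for ANCOVA on baseline and age, if relations are linear.

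The mean gap among those above 0.5 SD is about 0.69 SD, so the conditional bias is:

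| Analysis | r = 0.2 | r = 0.5 | r = 0.7 |
|---|---|---|---|
| Unadjusted week 12 | 0.14 | 0.35 | 0.48 |
| Change score | 0 | 0 | 0 |
| Baseline ANCOVA, ρ = 0.7 | 0.04 | 0.10 | 0.14 |
| Baseline ANCOVA, ρ = 0.8 | 0.03 | 0.07 | 0.10 |
| Baseline + age | 0 | 0 | 0 |

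**5. Power at d = 1.09, 12 per arm.** With k covariates, the noncentrality is 1.09 × √6 × √(1 − k/22) / √(1 − R²) on 22 − k df. R² is r² (age), ρ² (baseline), or (ρ² + r² − 2ρr²)/(1 − r²) (both).

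| Model | r = 0.2 | r = 0.5 | r = 0.7 |
|---|---|---|---|
| Unadjusted | 0.723 | 0.723 | 0.723 |
| Age only (the GAS case) | 0.719 | 0.819 | 0.936 |
| Baseline, ρ = 0.7 | 0.936 | 0.936 | 0.936 |
| Baseline + age, ρ = 0.7 | 0.925 | 0.937 | 0.961 |
| Baseline, ρ = 0.8 | 0.985 | 0.985 | 0.985 |
| Baseline + age, ρ = 0.8 | 0.981 | 0.984 | 0.989 |

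Once the baseline score is in, adding age changes power by between about −0.01 and +0.03. If age is unrelated to the scores (r = 0 in the same formula), it costs 0.723 − 0.701 = 0.02 without a baseline term, and 0.936 − 0.924 = 0.01 or 0.985 − 0.981 = 0.004 with one.

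**6. Type I error.** Over all randomisations it is about 0.05 in every model. Given an age gap above 0.5 SD, it is about 0.06, 0.10 and 0.15 for the unadjusted week-12 test at r = 0.2, 0.5 and 0.7. For baseline ANCOVA it is 0.055 to 0.073 at r = 0.5 to 0.7.

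**The case against.** The strongest reply is that the demographic tests change no outcome result. The SAP already plans descriptive statistics, and a superfluous column of p-values is a matter of reporting style. A reader might infer that the plan uses these tests in place of adjustment, or would adjust only if one were significant. The SAP says neither, so that inference is not supported.

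A reader might also infer that leaving age out biases the arm comparison by 0.35 to 0.48 SD, lifts the false positive rate to 0.10 to 0.15, and forgoes a rise in power from 0.72 to 0.82 or 0.94 for every score. Those figures compare a week-12 score analysed without its baseline against one adjusted for age alone. The plan's first primary outcome is a change and its outcome test is pre versus post. A between-arm comparison of change scores would have almost no such bias when age correlates equally with both scores. The error rates also apply only to the 22% or so of randomisations with a large gap. This part of the objection stands.

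Three further limits also stand. The age-score correlation is not documented, and it would be smaller if Bayley scores are age-normed, which the documents do not say. The age on the form could be a parent's, although corrected age has to be worked out to judge eligibility. Linear ANCOVA in 24 infants is a step away from a rank-based plan and needs a check.

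None of this supplies the missing between-arm model, or makes a demographic p-value informative with 12 per arm.

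**Conclusion.** The point holds as an inexpensive improvement. It does not show that the planned tests would be invalid. The demographic tests are uninformative about comparability: they miss about 80% of age gaps above 0.5 SD, and that figure hardly depends on the shape of the age distribution. The larger omission is the between-arm outcome model itself, where the baseline score does most of the work: power about 0.72 without it, and about 0.94 to 0.985 with it at ρ = 0.7 to 0.8.

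For HINE and Bayley III, corrected age is a modest addition: essentially neutral for power, and removing about 0.03 to 0.14 SD of conditional bias when the arms differ in age by more than 0.5 SD. For GAS, where the proposed model has no baseline term, age could matter more: a gain of about 0.10 in power at r = 0.5 and none at r = 0.2. The bias and power figures rest on assumed correlations and linear relations. Only the imbalance and detection rates follow closely from the 12 per arm.

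**What to change.** In section 8:

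1. Replace the between-arm tests of demographics with a descriptive table by arm, without p-values. Standardised differences may be shown.
2. Prespecify a between-arm model for each score, fitted whatever the observed balance. For HINE and Bayley III: ANCOVA of the week-12 score on arm, baseline score and corrected age at baseline. For GAS: arm and corrected age.
3. Add a rank-based version of each model as a sensitivity analysis.
4. State whether Bayley III scores are raw or age-normed, and confirm that the infant's corrected age is recorded as a variable.

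The cost is SAP wording. Corrected age is needed for eligibility, and baseline scores are already due under the assessment schedule. Each covariate uses one degree of freedom; if age proves unrelated to a score, the loss of power is at most about 0.02.

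### The primary outcomes are assigned only a paired before-after test, so the plan specifies no comparison of the randomised arms

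*Combined protocol and SAP*

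**What the plan says.** Section 3 describes the study as "A prospective, randomized, controlled trial conducted at the Risky Infants Polyclinic", with two arms and this timetable: "12 weeks, with evaluations conducted at baseline, 4th, 8th, and 12th weeks". Secondary objective 1 in Section 2 is to "Compare the motor, cognitive, and language developmental progress of infants in telerehabilitation and single-session education groups". Section 5 names HINE, Bayley III and GAS as the primary outcomes.

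In Section 8, the Group Comparisons heading has two test lines. One concerns baseline characteristics and reads "Mann-Whitney U and chi-square tests for continuous and categorical demographic data". The other is the only line that names a test for the outcomes, and it reads "Wilcoxon Signed-Ranks Test for pre- and post-treatment comparisons of Bayley III, HINE, and GAS scores".

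No other line in the document gives a between-arm test, a comparison of change scores, a model or a treatment-effect estimate for any outcome.

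**The concern.** The signed-rank test is a paired test. Run separately in each arm, it asks whether that arm changed. Run on all infants pooled, it asks whether infants changed overall. Neither compares two independent arms, and the plan does not say which is meant.

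The enrolled infants are 0-12 months old by corrected age and are followed for 12 weeks. Section 3 gives both arms exercise training in the clinic, and the exercise instruction in Section 6 is not limited to one arm. A before-after change therefore mixes maturation, the exercises and any contribution of telerehabilitation. Only the randomised contrast can isolate the last of these.

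The stated analysis cannot answer secondary objective 1. Nor can it credit an improvement to telerehabilitation, as the primary objective requires. The likely way to fill the gap is to observe that one arm reached p<0.05 and the other did not. That is not a valid test of the difference between arms, and its error rate is not controlled.

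**Working it through.** **1. The plan's own figure.** Section 8 gives 24 infants (12 per group) for effect size 1.09, α = 0.05 and power 0.95. The type of effect size, the test family and the sidedness are not stated. The effect size is read here as a standardised mean difference or mean change.

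- Two independent groups, two-sided t-test, 12 per group: noncentrality = 1.09 × √(12/2) = 2.67 on 22 df, power 0.72. Reaching 0.95 takes 23 per group (46 in total). The one-sided version has power 0.83 and needs 19 per group.
- Paired test, n = 12: noncentrality = 1.09 × √12 = 3.78. A one-sided signed-rank test (efficiency 3/π relative to the t-test) has power 0.96 and needs 12. A two-sided paired t-test has power 0.93 and needs 14.

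The stated number does not reproduce as a two-arm comparison. The closest match is a one-sided paired test with 12 infants. That does not prove how the sponsor did the calculation.

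**2. What the planned test shows when telerehabilitation adds nothing.** Inputs: 12 infants per arm (Section 8), the signed-rank test (Section 8), and p<0.05 taken as two-sided (an assumption). Also assumed: normally distributed change scores with the same mean gain in both arms, in SD units of change. The documents give no gain, so a range is shown. The exact test at n = 12 is significant when the smaller rank sum is 13 or less out of 78.

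Let p be the chance that one arm is significant. The arms are independent, so P(telerehabilitation significant, control not) = p(1 − p). For example, at 0.5 SD this is 0.315 × 0.685 = 0.216. Simulation gives:

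| Shared gain (SD of change) | One arm significant, p | Telerehabilitation arm only, p(1 − p) |
|---|---|---|
| 0.25 | 0.11 | 0.10 |
| 0.5 | 0.31 | 0.22 |
| 0.7 | 0.55 | 0.25 |
| 1.0 | 0.85 | 0.13 |
| 1.09 | 0.90 | 0.09 |
| 1.5 | 0.99 | 0.006 |

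A Mann-Whitney test on change between the arms rejects in about 4% to 5% of trials at every gain tried, in either direction. About half of that favours telerehabilitation.

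**3. Several scores.** Take five scores (HINE, three Bayley III domains, GAS) with an assumed correlation of 0.5. The chance that at least one is significant in the telerehabilitation arm only is about 55% at 0.5 SD, 61% at 0.7 SD, 38% at 1.0 SD and 3% at 1.5 SD. At 0.7 SD it is 76% with correlation 0 and 49% with correlation 0.8. The fair benchmark is five between-arm Mann-Whitney tests with correlation 0.5, which favour telerehabilitation at least once in about 8.5% of trials.

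**The case against.** The strongest reply is that a comparison was intended and the drafting is terse. The heading is Group Comparisons, secondary objective 1 is comparative, and Mann-Whitney U is already among the named tests. This stands as a point of wording: the comparison is not specified, which is different from a decision not to make it. It does not rescue the plan. The demographic line restricts the unpaired tests on any natural reading, and an analyst who followed Section 8 would never compare outcomes between arms.

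The objections to the size of the problem also have force:

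- p(1 − p) cannot exceed 0.25, and a gain of 0.7 SD sits almost at that maximum. With strong maturation the one-arm-only pattern nearly disappears. Both arms are then significant, however, so the test still says nothing about telerehabilitation.
- The plan does not say whether scores are raw or age-standardised. If they are standardised, maturation could be small, so a significant before-after change is possible but not assured.
- The plan never says it would infer benefit from significance in one arm only. That is a foreseeable use of the results, not a stated rule.

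**Conclusion.** The concern holds. As written, no primary outcome has a comparison of the randomised arms, and the paired test cannot supply one. This conclusion rests on the text alone.

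The size of the resulting error depends on assumptions that the documents do not settle: equal gains in both arms, normal changes, two-sided testing and, for several scores, the correlation. Over shared gains of 0.25 to 1.5 SD, a telerehabilitation arm with no added benefit is significant before-after in 11% to 99% of trials. It alone is significant in under 1% to about 25%. A test between the arms holds its level of about 4% to 5% over the same range. The plan must be changed before effectiveness claims rest on it.

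**What to change.** For HINE, each Bayley III domain and GAS, specify a comparison between the arms at week 12. Use a baseline-adjusted difference (ANCOVA) or, at minimum, a Mann-Whitney test on change from baseline to week 12, with an effect estimate and 95% CI. Label the within-arm Wilcoxon tests as descriptive, and state that any effectiveness claim rests on the between-arm result. State the sidedness and whether scores are raw or age-standardised.

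The cost is SAP wording and a few lines of analysis, with no new data. There are three consequences to state openly:

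- **Power.** With 12 per group and an effect of 1.09, two-sided between-arm power is about 0.68 to 0.72, not 0.95. Baseline adjustment may recover some of this, but the documents give no pre-post correlation from which to say how much.
- **Multiplicity.** Five unadjusted between-arm tests with correlation 0.5 give a two-sided familywise error of about 17%. Name one outcome as decisive or add an adjustment.
- **Timing.** Parts of the document are in the past tense. If outcome data have already been seen, label the between-arm analysis as post hoc.

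### GAS, a primary outcome, is tested only within infants before and after treatment; it needs a between-arm comparison of week-12 attainment

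*Combined protocol and SAP*

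**What the plan says.** Section 5 of the combined protocol and SAP lists GAS as the third primary outcome: "Goal achievement using the Goal Attainment Scale (GAS". Section 7 describes the instrument in one line: "Tracks individualized treatment goal achievement". Section 3 describes a randomised, controlled trial of two arms, "12 weeks, with evaluations conducted at baseline, 4th, 8th, and 12th weeks".

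Under Group Comparisons in Section 8, the only method that mentions GAS is "Wilcoxon Signed-Ranks Test for pre- and post-treatment comparisons of Bayley III, HINE, and GAS scores". The two-sample tests in the same list are limited to baseline characteristics: "Mann-Whitney U and chi-square tests for continuous and categorical demographic data".

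The documents do not state how many goals each infant has, whether that number is fixed, how the starting level is set, whether goals may be revised at weeks 4 or 8, or how GAS is scored. They also do not say whether the signed-rank test is run in each arm or on all infants together.

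**The concern.** The primary objective in Section 2 is to evaluate the effectiveness of the telerehabilitation approach. The evidence for that in this design is the contrast between the randomised arms. A signed-rank test pairs each infant with itself and leaves the contrast out.

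For GAS the gap has a feature of its own. The outcome is achievement of goals written for the individual infant. Such a goal describes something the infant does not yet do, so the natural movement from the start is upward, with or without the programme. Bayley III and HINE differ in that they measure the infant's status at every visit.

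If the plan is followed as written, the trial reports a GAS p-value on a primary outcome that mixes any programme effect with maturation and with goals that began unmet. A significant value could be read as evidence for telerehabilitation when the single-session arm moved just as far.

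**Working it through.** **1. Which question each test answers.** The signed-rank test asks whether scores moved between two times within the same infants. The two-sample tests in Section 8 could ask whether the arms differ, but they are assigned to demographic data. No listed method asks whether GAS differs between arms. This step needs no assumption.

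**2. How easily the within-arm test becomes significant (illustration).**

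Inputs: 12 infants per arm (Section 8, Sample Size Calculation) and significance at p<0.05 (Section 8), taken as two-sided. Assumptions not in the documents: five levels from -2 to +2, every infant starting at -2, one goal per infant, and no dropout.

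From the floor, every non-zero difference is positive. With m infants improving, the exact two-sided signed-rank p-value is 2/2^m:

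- m = 5: 2/32 = 0.0625
- m = 6: 2/64 = 0.031
- m = 12: 2/4096 = 0.0005

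Six of 12 is therefore enough. If each infant improves with probability p for any reason, the chance of significance in one arm is P(X ≥ 6), with X binomial(12, p):

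| p | Chance of significance in one arm |
|---|---|
| 30% | 12% |
| 40% | 33% |
| 50% | 61% |
| 60% | 84% |
| 70% | 96% |

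**3. Reading one arm against the other does not repair this.** Suppose that the arms are truly identical with p = 50%. The chance that exactly one arm is significant is 2 × 0.613 × 0.387 = 0.47. A significant result in one arm and not in the other is then common without any treatment difference.

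**4. Sensitivity to the starting level.** If infants start at -1, with a 10% chance of falling one level and a 50%, 60% or 70% chance of rising one level, the chance of significance in one arm is 29%, 45% or 60%. With a 25% chance of falling and 25% of rising it is about 1%. The size of the problem therefore depends on a starting rule that the plan does not give.

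**5. Which score to compare at week 12.** Take the usual T-score with equal weights and an assumed inter-goal correlation of 0.3. With k goals all at level x, T = 50 + 10kx/√(0.7k + 0.3k²):

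| Level on every goal | 1 goal | 2 goals | 3 goals |
|---|---|---|---|
| -1 | 40.0 | 37.6 | 36.3 |
| 0 | 50.0 | 50.0 | 50.0 |
| +1 | 60.0 | 62.4 | 63.7 |

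At any common level other than 0, infants with the same attainment score differently if their number of goals differs. The mean level across goals is -1, 0 or +1 whatever the number of goals.

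**6. Precision of the between-arm test.** Section 8 states that "the effect size was calculated as 1.09" and that "a total sample size of 24 infants (12 per group) was determined for α =0.05 and power=0.95". Taken as a standardised mean difference, 1.09 with 12 per group gives two-sided power of 0.72 for a t-test, or 0.70 for Mann-Whitney (relative efficiency 3/π), not 0.95. Power of 0.95 needs 23 or 24 per group. This is a separate matter and does not decide the present point, but the sponsor should know it before adopting the fix.

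**The case against.** **The test may be meant as description.** Section 2 places GAS among the secondary objectives, with the aim of determining whether individual goals are reached, and a pre/post summary would serve that aim. This does not remove the problem, because Section 5 makes GAS a primary outcome and Section 8 gives it a significance test and no other analysis. The signed-rank line does stand under a Group Comparisons heading, but that does not turn a paired test into a comparison of arms.

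**The same gap affects HINE and Bayley III.** This is true. They share the line and also lack a between-arm test. The point for GAS still needs its own repair, because its score must be tied to the goals set at baseline and its scoring rule must be stated.

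**A reader might infer that a positive GAS test is close to guaranteed.** The documents do not support that. They give no starting level. Even from the floor, the chance is 12% when infants have a 30% chance of improving, and it is lower where worsening is possible.

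**A reader might infer that a GAS change score necessarily depends on the number of goals.** That requires both a T-score type of formula and a number of goals that varies between infants, and the plan states neither. With a mean level the dependence disappears. If the baseline really were the same constant for every infant, comparing change and comparing week-12 scores between arms would be the same analysis.

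**Conclusion.** The point holds. Section 8 analyses a primary outcome of a randomised trial only within infants, and the resulting p-value cannot separate the programme from maturation or from goals that start unmet. That conclusion rests on the text alone.

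Its numerical size is conditional. The 12%, 61% and 96% figures assume 12 analysed infants per arm, one goal each, a start at the lowest level and an exact two-sided test. They show that significance can be likely with no programme effect, not that it is assured. Dependence on the number of goals bears on the choice of score for the repaired analysis; it is not a demonstrated fault of the present one.

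**What to change.** In Section 8, remove GAS from the pre/post Wilcoxon line as an efficacy test; within-arm GAS changes can be reported descriptively. Add as the primary GAS analysis:

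- a between-arm Mann-Whitney comparison of week-12 attainment, scored against the goals set at baseline;
- a Hodges-Lehmann difference between arms with its 95% confidence interval;
- the score defined as the mean attainment level across an infant's goals or, if a T-score is preferred, the same fixed number of goals for every infant.

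State the number of goals, how the starting level is set, and the scoring formula.

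The cost is SAP wording, because week 12 is already an evaluation visit and no new one is needed. One condition applies: if goals were rewritten at weeks 4 or 8, attainment of the baseline goals must still be recoverable at week 12, and the sponsor should confirm this. The sponsor gives up a within-arm p-value that may be easy to make significant, in exchange for a comparison that, at 12 per group and an effect of 1.09, has about 70% power.
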